2.7.3 Handling of missing values/censoring/discontinuations

ORR

See [Section 2.5.2.3](#).

TTR

Subjects who did not achieve a confirmed PR or CR will be censored as described in [Section 2.7.1](#).

DOR

Subjects continuing without progression or death will be censored at the date of their last adequate tumor assessment using the censoring rule described for the PFS analysis.

PFS

PFS will be censored at the date of the last adequate tumor assessment if no PFS event is observed prior to the [REDACTED] analysis cut-off date or before the start of the new anti-cancer therapy date, whichever is earlier.

The date of last adequate tumor assessment is the date of the last tumor assessment with overall lesion response of CR, PR or SD before an event or a censoring reason occurred. In this case the last tumor evaluation date at that assessment will be used. If no post-baseline assessments are available (before an event or a censoring reason occurred) then the start date of treatment will be used.

In particular, PFS will be censored at the last adequate tumor assessment if one of the following occurs: absence of event; the event occurred after a new anti-cancer therapy was administered (see also [Section 2.5.2.3](#)); the event occurred after two or more missing tumor assessments.

The term ‘missing adequate tumor assessment’ is defined as a TA not performed or TA with overall lesion response of ‘UNK’. The rule to determine the number of missing TAs is based on the time interval between the date of last adequate tumor assessment and the date of an event. If the interval is greater than twice the protocol-specified interval between the TAs and 2 times the protocol-allowed time window around assessments, then the number of missing assessments will be 2 or more.

Refer to [Table 2-4](#) for censoring and event date options and outcomes for PFS.

Table 2-4 Outcome and event/censor dates for PFS analysis

Situation	Date	Outcome
No baseline assessment	Start date of treatment	Censored
Progression or death at or before next scheduled assessment	Date of progression (or death)	Progressed
Progression or death after exactly one missing assessment	Date of progression (or death)	Progressed
Progression or death after two or more missing assessments	Date of last adequate assessment prior to missed assessment	Censored
No progression (or death)	Date of last adequate assessment	Censored

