- End dates
 - If day is missing, imputed date = min(reference end date, last day of the month)
 - If month and day are missing, imputed date = min(reference end date, 31Dec)

Reference end date will be the start date of study treatment.

If the end date is not missing and the imputed start date is after the end date, use the end date as the imputed start date. If both the start date and the end date are imputed and if the imputed start date is after the imputed end date, use the imputed end date as the imputation for the start date.

Post-treatment antineoplastic therapies date imputation

For new antineoplastic (ANP) therapies starting after study treatment was discontinued or starting while study treatment was still ongoing (protocol deviation), a missing or partial start date of this new therapy will be imputed as specified in [Table 5-3](#).

The complete (imputed) dates are required for censoring of efficacy endpoints. Therefore, partial or missing start dates will only be imputed for the first such therapy. Partial or missing end dates of the first new therapy and any partial or missing dates of second or later new antineoplastic therapies will not be imputed.

Table 5-3 Imputation of start dates for post-treatment antineoplastic medications

Missing element	Rule
Day	
 • If available year \geq year of study treatment end date then ANP start date = max(study treatment end date + 1, 01MonYYYY) • If available year < year of study treatment end date then ANP start date = max(study treatment start date + 1, 01MonYYYY)
Day, month	
 • If available year = year of study treatment end date then ANP start date = min(study treatment end date + 1, 31DecYYYY) • If available year > year of study treatment end date then ANP start date = 01JanYYYY • If available year < year of study treatment end date, 
 • If available year < year of study treatment start date, do not impute • If available year > year of study treatment start date, then ANP start date = 01JulYYYY • If available year = year of study treatment start date and day/month of study treatment start date < 01JulYYYY, then ANP start date = 01JulYYYY

Missing element	Rule
	
 If available year = year of study treatment end date and day/month of study treatment start date \geq 01JulYYYY, then ANP start date = min(middle between the treatment start and end date, 31DecYYYY)

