Day, month, and year	For completely missing start dates, set to study treatment end date + 1

If the end date is not missing and the imputed start date is after the end date, use the end date as the imputed start date.

In case there are any scenarios found in the final data that are not covered by the rules above, they will be handled in the respective dataset program and documented in the PDS.

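### Table 5-3 imputes an incomplete start date of new anti-cancer therapy without looking at documented progression, so some progressions after last dose are censored instead of counted in PFS and DOR

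*SAP*

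**What the plan says.** Section 5.1.3 imputes the start date of the first new antineoplastic therapy only, and gives the purpose: "The complete (imputed) dates are required for censoring of efficacy endpoints". The branches of Table 5-3 that matter for therapy begun after study treatment are:

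- **Nothing recorded:** "For completely missing start dates, set to study treatment end date + 1".
- **Year only, equal to the treatment-end year:** treatment end + 1, capped at 31 December.
- **Year only, later:** "If available year > year of study treatment end date then ANP start date = 01JanYYYY".
- **Day missing, year at or after the treatment-end year:** the later of treatment end + 1 and the first of the recorded month.

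Year-only dates before the treatment-end year follow other rules (1 July or a midpoint). They concern therapy started during study treatment and are outside this point.

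Section 2.7.3 censors PFS at the last adequate tumor assessment when "the event occurred after a new anti-cancer therapy was administered". Table 2-4 places that assessment on or before the start of the new therapy. DOR follows the PFS rule (sections 2.7.1 and 2.7.3).

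**The concern.** No branch of Table 5-3 uses the date of documented progression. For therapy begun after study treatment, the four branches above each pick the earliest day that the record allows. Suppose a subject stops treatment, has a RECIST progression on a later scan, and then starts next-line therapy whose date is incompletely recorded. The imputed start can fall before the scan although the real start came after it, and a documented progression becomes a censoring because of a gap in data entry.

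The censoring time then sits just ahead of a known progression. That is informative censoring, and it tends to push the Kaplan-Meier estimates of PFS and DOR upward.

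Nothing else in section 5.1.3 catches this. The one check compares the imputed start with the therapy's own end date and can only move the start earlier. The catch-all for uncovered scenarios does not apply, because these cases are covered. The same section does protect the order of events when it imputes diagnosis and recurrence dates.

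**Working it through.** The SAP gives no event count or proportion of incomplete dates, and section 3 refers to the Primary CSR for sample size. There is therefore no stated figure to reproduce. The rules were applied to worked dates, reading the treatment end date as the date of last dose.

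**1. Invented dates.** Last dose 10 Mar 2017, progression 28 Mar 2017, true therapy start 18 Apr 2017. With the true date, the progression is an event.

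| Recorded start | Imputed start | PFS outcome |
|---|---|---|
| nothing | 11 Mar 2017 | censored |
| 2017 | 11 Mar 2017 | censored |
| Apr 2017 | 1 Apr 2017 | event kept |

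**2. Dates from section 2.1.4.** The SAP's own example has last exposure on 31 Dec 2014 and discontinuation on 6 Jan 2015. Assume a progression scan on 6 Jan 2015. A start date that is blank, 2015, or Jan 2015 is imputed as 1 Jan 2015 and the event is censored. Feb 2015 or 2016 keeps the event.

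**3. A long gap.** Last dose 15 Feb 2018, progression 20 Aug 2018, therapy recorded as 2018. The imputed start is 16 Feb 2018. The progression is lost, with nearly all of the 186 days from last dose to progression.

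**4. Share of post-dose progressions lost, by date part missing.** Let g be the days from progression to new therapy. With only the day missing, the event is at risk when both dates fall in the same month, with probability about 1 - g/30.4375. For g = 7, 14, 21, 28 this gives 0.77, 0.54, 0.31, 0.08. That counts a progression on the imputed day as lost. Keeping it as an event gives 1 - (g + 1)/30.4375 = 0.74, 0.51, 0.28, 0.05. A simulation with progression 2 to 28 days after last dose (assumed), keeping same-day cases as events, gives:

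| Missing part | g = 7 | 14 | 21 | 28 |
|---|---|---|---|---|
| everything | 100% | 100% | 100% | 100% |
| day and month | 98% | 96% | 94% | 92% |
| day only | 74% | 51% | 28% | 5% |

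**5. Events lost in a group of 40.** Assume that 7 of 40 progress after last dose and get further therapy, and that 10-30% of those start dates are incomplete. Incomplete dates: 7 × 0.10 = 0.7 to 7 × 0.30 = 2.1.

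- All completely missing: 0.7 to 2.1 events lost.
- All with only the day missing: 0.7 × 0.08 = 0.06 to 2.1 × 0.77 = 1.6. If same-day cases are kept, the low end is 0.7 × 0.05 = 0.04.

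The results scale in proportion to the assumed 7.

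**6. Effect on the median.** Assumptions: n = 40, exponential PFS, 8-week scans, 24-48 months of follow-up, and each lost event censored one scan earlier. The table gives the mean of simulated Kaplan-Meier medians in months, by share of progressions lost.

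| True median | 0% | 5% | 10% | 20% |
|---|---|---|---|---|
| 9 | 9.8 | 10.5 | 11.0 | 12.1 |
| 12 | 12.7 | 13.6 | 14.4 | 16.0 |
| 18 | 18.7 | 19.9 | 21.2 | 23.5 |

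The 0% column already exceeds the true median, mainly because progression is dated at the next scan. The relevant comparison is along each row. The top of step 5 is 2.1/40 = 5.25% of subjects, so the 5% column is the closest match; the 10% and 20% columns need heavier losses than step 5 assumes.

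**The case against.** **The scope is narrow.** Progressions on or before last dose are untouched. So are those before the first day of a recorded later month or year. Same-day cases are unclear: section 2.7.1 looks for an event before the therapy start, while section 2.7.3 and Table 2-4 censor only an event that follows it. All of this stands.

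**Early dating is defensible for response.** The same therapy date limits which scans count for BOR (section 2.5.2.3). An early date can only exclude scans, so it cannot inflate ORR, the primary endpoint for Groups 1 to 3. This stands, and the rule should be left alone there.

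**A progression-dependent rule has its own bias.** Take two subjects with blank therapy dates and equal follow-up. The one who progresses is counted at progression; the one who does not is still censored near last dose. Events are kept while event-free time is cut, which pulls PFS downward. Investigator and BIRC progression dates can also differ. Both points stand and shape the fix.

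**The consequences are limited.** PFS and DOR are secondary and descriptive in a non-randomised study, and section 2.7.2 tabulates censoring for new therapy. That table does not separate imputed from recorded dates and does not restore events. Section 2.5.2.4, on supportive analyses, is not in the public text, so whether it holds a relevant sensitivity analysis cannot be judged.

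**Stronger readings.** A reader might infer that every incomplete date costs an event, or that one or two events are lost in each group. The documents support neither. The loss depends on which date part is missing, the inputs are assumed, and Group 2 has only about 5 subjects and Group 4 about 30. Nor does every endpoint move upward, since dropped scans can lower ORR.

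**Conclusion.** The point holds in this limited form. As written, Table 5-3 with section 2.7.3 can censor a RECIST progression documented after last dose, although the recorded date parts allow the new therapy to have started after it. PFS and DOR then lose a real event and tend to be biased upward.

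The number affected cannot be derived from the SAP. Under the assumed 7 of 40 and 10-30% incomplete dates, it lies between about 0.06 and 2.1 events in a group of 40. The upper end needs the incomplete dates to be blank or nearly so. The primary endpoint is not inflated. This is a worthwhile, inexpensive correction to a secondary analysis.

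**What to change.** Add to Table 5-3, for PFS and DOR only:

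- If a RECIST progression by the assessor being analysed (investigator or BIRC, each separately) is documented after last dose, and the recorded date parts and known therapy end date allow a later therapy start, impute the start as the day after that progression. Cap it at the end of the recorded month or year and at the known end date.
- A progression on the same day as the therapy start counts as an event.
- In all other cases the present rules apply, and they stay unchanged for BOR and ORR.

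Report PFS and DOR under the present rule as a sensitivity analysis. List every subject whose event or censoring status depends on an imputed therapy date.

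**Cost.** One further condition in the imputation program, an assessor-specific therapy date, a repeat of the PFS and DOR outputs, and one listing. A progression that truly followed new therapy may be counted as an event, and subjects without progression are still censored early, so the revised rule can bias PFS slightly downward. Showing both versions bounds the effect of this choice.

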5.2 AE coding/grading

Adverse events are coded using the MedDRA terminology. The latest available MedDRA version at the time of the analyses will be used and the version will be specified in the CSR as well as in a footnote in the applicable tables and listings.

AEs will be assessed according to CTCAE version 4.03.

The CTCAE represents a comprehensive grading system for reporting the acute and late effects of cancer treatments. CTCAE grading is by definition a 5-point scale generally corresponding to mild, moderate, severe, life threatening, and death. This grading system inherently places a value on the importance of an event, although there is not necessarily proportionality among grades (a grade 2 is not necessarily twice as bad as a grade 1).

5.3 Laboratory parameters derivations

5.3.1 CTC grading for laboratory parameters

Grade categorization of lab values will be assigned programmatically as per CTCAE version 4.03. The calculation of laboratory CTC grades will be based on the observed laboratory values only, clinical assessments will not be taken into account. The criteria to assign CTCAE grades are given in Novartis internal criteria for CTCAE grading of laboratory parameters. The latest available version of the document based on the underlying CTCAE version 4.03 at the time of analysis will be used. For laboratory tests where grades are not defined by CTCAE version 4.03, results will be graded by the low/normal/high classifications based on laboratory normal ranges.

A severity grade of 0 will be assigned for all non-missing lab values not graded as 1 or higher. Grade 5 will not be used. For laboratory tests that are graded for both low and high values, summaries will be done separately and labelled by direction, e.g., sodium will be summarized as hyponatremia and hypernatremia.

5.3.2 Imputation rules

CTC grading for blood differentials is based on absolute values. However, this data may not be reported as absolute counts but rather as percentage of WBC.

If laboratory values are provided as '<X' (i.e. below limit of detection) or '>X', prior to conversion of laboratory values to SI unit, these numeric values are set to X.

The following rules will be applied to derive the WBC differential counts when only percentages are available for an xxx differential:

$$\text{xxx count} = (\text{WBC count}) \times (\text{xxx \%value} / 100).$$

Further derivation of laboratory parameters might be required for CTCAE grading. For instance, corrected calcium can be derived using the reported total calcium value and albumin at the same assessment using the following formula:

$$\text{Corrected Calcium (mg/dL)} = \text{Calcium (mg/dL)} - 0.8 \times [\text{Albumin (g/dL)} - 4].$$

In order to apply the above formula, albumin values in g/L will be converted to g/dL (by multiplying by 0.1), calcium values in mmol/L will be converted to mg/dL by dividing by 0.2495. For calculation of laboratory CTC grades 0 and 1, the normal range for derived corrected calcium is set to the same limits (in mg/dL) as for calcium.

CTC grades for the derived absolute WBC differential counts (neutrophils, lymphocytes) and corrected calcium will be assigned as described above for grading.

5.4 Statistical models

5.4.1 Phase Ib

Refer to the [\[Primary CSR\]](#) for details.

Kaplan-Meier estimates

An estimate of the survival function in each treatment group, subgroup or overall will be constructed using the Kaplan-Meier (product-limit) method as implemented in SAS PROC LIFETEST with METHOD=KM option. The PROC LIFETEST statement will use the option CONFTYPE=LOGLOG.

Median survival for each treatment group, subgroup or overall will be obtained along with 95% confidence intervals calculated from PROC LIFETEST output using the method of [\[Brookmeyer and Crowley 1982\]](#). Kaplan-Meier estimates of the survival function with 95% confidence intervals at specific time points will be summarized. The standard error of the Kaplan-Meier estimate will be calculated using Greenwood's formula ([\[Collett 1994\]](#)).

Confidence interval for response rate

Responses will be summarized in terms of percentage rates with 95% CIs. An exact binomial confidence interval (implemented using SAS procedure FREQ with EXACT statement for one-way tables) will be calculated ([\[Clopper and Pearson 1934\]](#)).

6 References

Brookmeyer R and Crowley J (1982). A Confidence Interval for the Median Survival Time. *Biometrics*; 38:29-41.

Clopper CJ and Pearson ES (1934). The use of confidence or fiducial limits illustrated in the case of the binomial. *Biometrika*; 26:404-413.

Collett D (1994). *Modelling survival data in medical research*. London, Chapman & Hall.

European Medicines Agency (2021). *Guidance on the management of clinical trials during the COVID-19 (coronavirus) pandemic (Version 4.0)*.

Food and Drug Administration (2020). *FDA Guidance on Conduct of Clinical Trials of Medical Products during COVID-19 Pandemic: Guidance for Industry, Investigators, and Institutional Review Boards (September 2020)*.
